1.1. Mechanism of Action/Indication

Rivaripansel is being developed as a pan-selectin antagonist for the treatment of VOC in subjects with SCD (including SCD-SS, SCD-SC, SCD-S β^+ -thalassemia, and SCD-S β^0 -thalassemia).

1.2. Background and Rationale

1.2.1. Drug Development Rationale

Both P-selectin and E-selectin are responsible for the early recognition and adhesion of leukocytes to the vascular endothelium. L-selectin is located on a subset of leukocytes and participates in rolling and adhesion and plays a major role in homing to the lymph nodes.

By inhibiting the initial recognition, and thereby decreasing or preventing stickiness of RBC/WBC/endothelial cells in SCD, the pathophysiologic process of VOC may be interrupted and/or prevented. Damage caused by these infiltrating cells in an inflammatory response is therefore prevented and blood flow may be improved.

Rivipansel is a pan-selectin antagonist developed at GlycoMimetics that inhibits selectin binding *in vitro* as well as selectin-mediated effects *in vivo*. Inhibition of selectins offers potential promise as a useful therapeutic option for patients with SCD. Rivipansel has potent anti-inflammatory effects in a number of animal models, including the sickle cell mouse, in which it has been shown to normalize blood flow, reduce blood cell aggregation, and to improve survival in a model of VOC. In addition, the Phase 2 study (GMI-1070-201) data have shown that such effects in SCD patients have led to a reduction in the length and intensity of SCD pain crises. Treatment of VOC with mechanism-based therapies is an area of unmet medical need in both adult and pediatric patients with SCD. Both pediatric and adult patients would be expected to benefit substantially from a therapy that could treat VOC and therefore measurably reduce the associated suffering and adverse clinical outcomes.

1.2.2. Pre-Clinical Development of Rivipansel

For information on nonclinical pharmacology, pharmacokinetics and product metabolism in animals, and toxicology studies, please refer to the Investigator's Brochure.

1.2.3. Clinical Experience with Rivipansel

Clinical information is available from three completed Phase 1 studies, and a completed Phase 2 study, all conducted by GlycoMimetics. Additionally, data are available from a completed Pfizer sponsored Phase 1 study to assess the effect of rivipansel on corrected QT interval (QTc).

GlycoMimetic Studies

In the first Phase 1 study (GMI-1070-101), healthy volunteer subjects received single intravenous (IV) doses of 2, 5, 10, 20, or 40 mg/kg rivipansel or placebo. In the second Phase 1 study (GMI-1070-102), healthy volunteer subjects received multiple IV doses of 5, 10, or 20 mg/kg rivipansel or placebo every 8 hours for a total of 13 doses. An additional group of subjects received a loading dose of 40 mg/kg, followed by multiple doses of 20 mg/kg rivipansel every 8 hours for a total of 6 doses. These studies evaluated a total of 72 healthy adult subjects (54 active, 18 placebo).

Pharmacokinetic (PK) data are available from these studies in healthy volunteers. Mean values for C_{max} , area under the curve ($AUC_{(0-t)}$), and $AUC_{(inf)}$ increased in a dose-proportional manner, providing evidence of linear pharmacokinetics. After a single 20 minute infusion of 20 mg/kg, the mean \pm standard deviation C_{max} was 256 ± 43.7 mg/L. The time of peak concentrations corresponds to the time of the end of infusion and the collection of the first blood sample for determination of GMI-1070. The volume of distribution was consistent across dose levels, 0.130 to 0.181 L/kg. Clearance was consistent across dose levels (0.211 to 0.284 mL/min/kg) and the mean elimination half-life ($t_{1/2}$) ranged from 6.67 hours to

7.41 hours. Urine collection after the multiple dose administration showed a minimum of 89% of the dose was recovered intact in the urine, and CL_r was less than filtration clearance, consistent with tubular reabsorption.

The third Phase 1 study (GMI-1070-103) was an open-label study of IV rivilansel in 15 adult subjects with stable SCD who received a 20 mg/kg loading dose of IV rivilansel, followed 10 hours later by a 10 mg/kg dose of IV rivilansel. The pharmacokinetics were observed to be consistent with those in the healthy volunteers.

In these three Phase 1 studies there were no clinically significant electrocardiogram (ECG) or physical examination findings. With one exception, all adverse events in subjects receiving rivilansel were Grades 1 or 2. Severe symptomatic anemia (Grade 4) that occurred in 1 subject with stable SCD was considered to be remotely related to the study medication, and resolved with therapy. No serious adverse events were reported in these studies.

A randomized, placebo-controlled Phase 2 trial (GMI-1070-201), evaluating the efficacy, safety, and pharmacokinetics of multiple IV doses of rivilansel in 76 subjects 12 to 60 years of age who were hospitalized for sickle cell VOC is now complete. This study included two dosing schedules; the first cohort received 20 mg/kg loading dose, then 10 mg/kg every 12 hours for up to 7 days, (maximum 15 doses) and the second cohort received 40 mg/kg loading dose, then 20 mg/kg every 12 hours for up to 7 days, (maximum 15 doses).

In the phase 2 study, the primary endpoint, time to resolution of VOC, was shorter for the rivilansel treated group versus the placebo group. The mean time to VOC resolution was 110 hours and 148 hours for the rivilansel treated group and the placebo group, respectively. Treatment with rivilansel was also associated with improvement in clinical measures of VOC. The rivilansel treatment group had a shorter median time to transition from parenteral to oral pain medications, time to discharge from the hospital, and time to first sustained reduction in VAS pain score. Mean use of opioid analgesics during hospitalization was also lower in the rivilansel treated group.

Total treatment-emergent adverse event (TEAE) rates were comparable across groups. Serious Adverse Events (SAE) and those SAEs “related to treatment” were also comparable across groups. Eleven (11, 14.4%) subjects discontinued study drug treatment due to adverse events (8 [10.5%] subjects in the active group, and 3 [3.9%] subjects in the placebo group). No subjects discontinued participation in the study due to adverse events. A total of 28 serious adverse events (SAEs) were reported, encompassing 29 event terms across 23 subjects. A 30% SAE rate was seen in both active and placebo groups. The most common SAE in both treatment groups was re-hospitalization for VOC. One (1) SAE of acute generalized exanthematous pustulosis (AGEP) rash was seen in a subject who received the high dose; other less severe rash events were distributed across treated and placebo groups. No subjects died.

Of note, the drug product formulation that will be used in this study is a 30 mg/mL solution for injection in which the concentration is 30 mg/mL based on the active moiety of rivilansel. The drug product used in the Phase 1 and Phase 2 studies described previously (conducted by GlycoMimetics) was a 30 mg/mL solution for injection based on the salt of rivilansel which is equivalent to 28.28 mg/mL of the active moiety rivilansel.

Pfizer Sponsored Studies

A Phase 1 placebo and active controlled study to evaluate the effect of intravenous rivipansel on QTc interval in 48 healthy African-American adult subjects (Pfizer Study B5201001) has been completed. The rivipansel dose in the study was 4 grams (expressed as active moiety) as a single intravenous infusion and the active control was a single dose of moxifloxacin 400mg orally.

The study was deemed negative; the statistical analyses of the ECG measurements demonstrated a lack of a QTc effect with rivipansel compared to placebo as the upper bound of the 2-sided 90% confidence interval (CI) for mean differences between rivipansel and placebo at all 11 post-dose time points was below the International Council for Harmonisation (ICH) E14 criteria of 10 milliseconds (msec). The highest observed upper bound of the 2-sided 90% CIs was 3.22 msec at 3 hours post-dose. The moxifloxacin positive control performed as expected, thus the study should be deemed adequately sensitive.

1.2.4. Study Rationale

Rivipansel is a glycomimetic inhibitor of E-, P-, and L-selectins *in vitro*. Rivipansel has been shown to inhibit inflammation in several animal models of disease, including the mouse model of vaso-occlusive crisis (VOC) of sickle cell disease (SCD). It has also been shown to consistently improve multiple clinically meaningful measures of the VOC experience, for both the pediatric and adult subjects enrolled in the Phase 2 study (GMI-1070-201). This Phase 3 study will continue to examine rivipansel for the treatment of VOC in patients with SCD.

1.2.5. Dose Rationale

Rivipansel is administered intravenously. In this current Phase 3 study, rivipansel IV solution for injection contains 30 mg/mL of active moiety rivipansel.

The dosing regimen in this Phase 3 study is as follows:

- Subjects aged 12 and over who weigh >40 kg, will receive study drug as a loading dose of 1680 mg followed by a maintenance dose of 840 mg every 12 ± 2 hours.

- Subjects aged 6 to 11 years, or any subject who weighs ≤ 40 kg, will receive weight-based dosing (mg/kg) administered as a loading dose of 40 mg/kg (maximum of 1680 mg) followed by a maintenance dose of 20 mg/kg (maximum of 840 mg) every 12 ± 2 hours.

The selection of the dose in this Phase 3 study was based on efficacy, safety, and pharmacokinetic results from the Phase 2 study, where a low dose (20 mg/kg loading dose/10 mg/kg every 12 hours) and a high dose (40 mg/kg loading dose/20 mg/kg every 12 hours) were studied (the doses were studied in a sequential fashion). In the Phase 2 study, the differences between the median time to discharge for rivipansel and placebo treatment groups were similar for the low rivipansel dose (56 hours) and the high dose (55 hours). Phase 2 treatment-emergent adverse events (AEs) by dose, as well as other safety data, indicates there were no apparent safety differences for either the low or high dose relative to placebo. The pharmacokinetic data from the Phase 2 study support fixed flat dosing for subjects 12 years of age and above. Furthermore, fixed flat dosing is a common approach for the administration of small molecules with a favorable safety margin, and offers a simpler approach with the potential for fewer dosing errors. Pharmacokinetic modeling and simulations predict that the dose will result in exposures similar to that observed with the low dose in the Phase 2 study and a minimum plasma concentration above 10 μ g/mL will be maintained throughout the dosing interval. This concentration has shown improved blood flow, rolling flux and survival rate in a SCD mouse efficacy model.²³ In order for subjects ≥ 12 years of age not to exceed the high dose of 40/20 mg/kg studied in the Phase 2 study, the weight cut off was chosen to be 40 kg. Based on the similarity of efficacy and safety results between the 2 doses studied in the Phase 2 study, only a single dose will be studied.

Weight-based dosing for subjects 6 to 11 years of age will be used in this study. This is the most conservative approach given that children in this age range have not been previously studied. In the Phase 2 study, GMI-1070-201, subjects ≥ 12 years old with the regimen of 20 mg/kg loading dose followed by 10 mg/kg every 12 hours were studied and the dose was found to be efficacious. Because the exposures resulting from this dosing should result in similar efficacy in the younger subjects, modeling and simulation exercises were performed to identify dosing regimens that predict similar exposures. The simulations showed that for children 6 to 11 years old, a 40 mg/kg loading dose (maximum 1680 mg) followed by 20 mg/kg every 12 hours (maximum 840 mg) will result in concentrations similar to those observed with the 20/10 mg/kg dosing in the GMI-1070-201 study.

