Subjects with acute VOC who complete the VOC/Treatment-Ready screening assessments and meet all eligibility criteria are enrolled into the study and will be randomized in a 1:1 ratio to receive multiple IV doses of rivipansel or placebo for the treatment of VOC. Randomization will be stratified by age (6-11, 12-17, and ≥ 18 years of age) and genotype (category 1: HbSS, HbS β^0 thalassemia and HbSD; category 2: HbSC, HbS β^+ thalassemia and HbS-Variant [other than HbSD]).

Dosing of eligible subjects with acute VOC will be initiated as early as possible, but no later than 24 hours from the administration of the first dose of IV opioids. For subjects aged 12 and over who weigh >40 kg, study drug will be administered as a loading dose of 1680 mg followed by a maintenance dose of 840 mg every 12 ± 2 hours. Subjects aged 6 to 11 years, or any subject who weighs ≤ 40 kg, will receive a loading dose of 40 mg/kg (maximum of 1680 mg) followed by a maintenance dose of 20 mg/kg (maximum of 840 mg) every 12 ± 2 hours. Study drug will be administered until criterion 1 of the

readiness-for-discharge criteria (see below) has been met, or up to 15 doses of study drug (1 loading dose and a maximum of 14 maintenance doses), whichever comes first.

[figure not shown]
The primary endpoint is time to readiness-for-discharge, where readiness-for discharge is met when all of the applicable 6 criteria are documented to have occurred – the criteria are to be assessed in relation to treatment for this VOC event and acute complication(s) directly related to this VOC event:

1. Only oral pain medication is required.
2. Acute complications related to VOC (such as ACS, stroke, priapism) have resolved to the extent that management can be in an outpatient setting, if applicable.
3. IV opioids have been discontinued.
4. IV hydration has been discontinued, if applicable.
5. IV antibiotics have been discontinued, if applicable.
6. RBC transfusion is no longer required for the treatment of this VOC, if applicable.

The readiness-for-discharge criteria will be assessed in all subjects at pre-defined intervals (and ad hoc as necessary) from the start time of the loading dose until discharge. Readiness-for-discharge criteria should continue to be evaluated after they have been met until subjects have left the hospital, to ensure no subsequent updates to the readiness-for-discharge evaluations are required.

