5. STUDY TREATMENTS

For the purposes of this study, and per International Council on Harmonisation (ICH) guidelines, investigational product is defined as a pharmaceutical form of an active ingredient or placebo being tested or used as a reference/comparator in a clinical trial, including a product with a marketing authorization when used or assembled (formulated or packaged) in a way different from the approved form, or when used for an unapproved indication, or when used to gain further information about an approved use (ICH E6 1.33).

For this study, the investigational products are Rivipansel and a phosphate buffered saline Placebo.

Subjects will be randomized at a 1:1 ratio to one of two treatment groups:

- Rivipansel;
- Placebo.

Subjects aged 12 and over who weigh >40 kg, will receive a loading dose of study drug of 1680 mg followed by a maintenance dose of 840 mg every 12 ± 2 hours. Subjects aged 6 to 11 years, or any subject who weighs ≤40 kg, will receive weight-based dosing (mg/kg) administered as a loading dose of 40 mg/kg (maximum of 1680 mg) followed by a maintenance dose of 20 mg/kg (maximum of 840 mg) every 12 ± 2 hours. Study drug will be administered until criterion 1 of the readiness-for-discharge criteria (see [Section 7.1.1](#)) has been met, or up to 15 doses of study drug (1 loading dose and a maximum of 14 maintenance doses), whichever comes first.

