5.4.2. Preparation and Dispensing

The randomization system will identify the specific vials to be used to prepare the dose for each subject according to the randomization list.

Subjects aged 12 and over who weigh >40 kg, will receive a loading dose of 1680 mg followed by a maintenance dose of 840 mg every 12 ± 2 hours. Two vials will be assigned by the randomization system for the loading dose and a single vial for each of the subsequent maintenance doses.

Subjects aged 6 to 11 years, or any subject who weighs ≤ 40 kg, will receive a loading dose of 40 mg/kg (maximum of 1680 mg) followed by a maintenance dose of 20 mg/kg (maximum of 840 mg) every 12 ± 2 hours. The weight measured as part of the VOC/Treatment-Ready screening procedures will be used to determine the appropriate dose to be administered during the study.

Study drug will be administered until criterion 1 of the readiness-for-discharge criteria (see [Section 7.1.1](#)) has been met, or up to 15 doses of study drug (1 loading dose and a maximum of 14 maintenance doses), whichever comes first.

Active or placebo sterile solution for intravenous infusion will be prepared and stored according to details specified in the IP Handling Manual.

The unblinded pharmacist (or designee) will prepare the study drug and, as described in the IP Handling Manual, this will include the requirement for the study drug to be filtered upon transfer to the infusion bag or syringe through a 0.22 micron syringe filter. A second unblinded person on the study site staff must verify the correct dose was prepared prior to dispensing.

To avoid unblinding due to a potential color difference between the active and placebo solutions, only unblinded study site staff should open the vial cartons and prepare the dose.

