6.2. Study Period

6.2.1. Visit 1, Day 1 – Loading Dose

All subjects should be dosed with study drug as early as possible, but the start of study drug dosing should be no later than 24 hours from the administration of the first dose of IV opioids.

At this visit, the following will be performed:

1. Record adverse events.
2. Record concomitant medications, including parenteral opioid use. Record IV opioid use approximately every 4 hours for the first 48 hours from the start time of the study drug loading dose.
3. Record concomitant non-drug treatments/procedures.

[REDACTED]

5. Administer study drug infusion. Record the date and time (24-hour clock) of the beginning and the end of the infusion.

Dosing with study drug will continue every 12 (± 2) hours until the study drug is discontinued. For those subject 6 to 11 years old, or any subject $\leq 40\text{kg}$, the weight measured as part of the VOC/Treatment-Ready screening procedures will be used to determine the appropriate dose to be administered during the study. Study drug will be administered as described in [Section 5](#), Study Treatments.

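### On nominal milligrams, the flat 1680/840 mg dose meets the stated 40/20 mg/kg ceiling only from 42 kg, not from the 40 kg cut-off (minor)

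*Protocol*

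**What the plan says.** Protocol section 1.2.5 sets two regimens. Subjects aged 12 and over who weigh more than 40 kg "will receive study drug as a loading dose of 1680 mg followed by a maintenance dose of 840 mg" every 12 hours. Subjects aged 6 to 11, and anyone of 40 kg or less, receive 40 mg/kg then 20 mg/kg, capped at the same 1680 and 840 mg. The section then gives the reason for the threshold: subjects aged 12 and over are "not to exceed the high dose of 40/20 mg/kg studied in the Phase 2 study, the weight cut off was chosen to be 40 kg".

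The threshold is operative. Section 3.1 of the protocol states "For subjects aged 12 and over who weigh >40 kg, study drug will be administered as a loading dose of 1680 mg". Section 5, section 5.4.2 and SAP section 2.1 give the same rule, and protocol section 6.2.1 repeats the 40 kg limit for weight-based dosing.

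Two other statements bear on the size and consequence. Section 1.2.3 says that the Phase 1 and Phase 2 product was 30 mg/mL as the salt, equal to 28.28 mg/mL of active moiety, while the product for this study is 30 mg/mL of active moiety. Section 1.2.5 says that modelling and simulation "predict that the dose will result in exposures similar to that observed with the low dose in the Phase 2 study".

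**The concern.** A flat dose gives the most per kilogram to the lightest person who receives it. The cut-off therefore has to be at least the flat dose divided by the ceiling, and 40 kg is below that figure. The protocol expresses the ceiling as a limit not to be exceeded and states no tolerance or rounding allowance. Rounding a minimum weight downwards would in any case go the wrong way.

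What is at stake is the accuracy of a dose-limit statement. An ethics committee or regulator would read it as an assurance about the lightest adolescents and adults on the flat dose, and as written the assurance is not true for all of them.

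**Working it through.** **Inputs.** Flat dose 1680 mg loading and 840 mg maintenance; ceiling 40 and 20 mg/kg; cut-off above 40 kg (all protocol section 1.2.5). Salt-to-moiety ratio 28.28/30 = 0.9427 (protocol section 1.2.3).

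**Trying to reproduce the plan's 40 kg.** Minimum weight = flat dose / ceiling per kg.
- Loading: 1680/40 = 42.0 kg.
- Maintenance: 840/20 = 42.0 kg.
- A 40 kg cut-off would need a flat dose of at most 40 × 40 = 1600 mg and 40 × 20 = 800 mg.

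The stated figure is not reproduced. The caps on the weight-based regimen also bind at 42 kg.

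**Salt-based reading (assumption: the Phase 2 mg/kg doses were expressed as salt).**
- Ceiling in active moiety: 40 × 0.9427 = 37.71 mg/kg and 20 × 0.9427 = 18.85 mg/kg.
- Minimum weight: 1680/37.71 = 44.6 kg (the same for maintenance).

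**Reverse reading.** Treating the Phase 3 flat dose as salt and the ceiling as moiety gives 1680 × 0.9427/40 = 39.6 kg. Of the readings tried, only this one fits 40 kg, but it contradicts sections 1.2.3 and 1.2.5, which put Phase 3 on active moiety.

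**Excess by weight.** Excess = (flat dose / weight) / ceiling − 1.

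| Weight (kg) | Flat dose (mg/kg) | Excess, nominal | Excess, salt-based |
|---|---|---|---|
| 40 (limit, not reached) | 42.00/21.00 | +5.0% | +11.4% |
| 40.1 | 41.90/20.95 | +4.7% | +11.1% |
| 40.5 | 41.48/20.74 | +3.7% | +10.0% |
| 41 | 40.98/20.49 | +2.4% | +8.7% |
| 41.5 | 40.48/20.24 | +1.2% | +7.4% |
| 42 | 40.00/20.00 | 0 | +6.1% |
| 43 | 39.07/19.53 | −2.3% | +3.6% |
| 44.55 | 37.71/18.86 | −5.7% | 0.0% |

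The first row is a limit because a subject of exactly 40 kg is dosed by weight and receives 1600/800 mg. Crossing 40 kg therefore adds a step of 80 mg loading and 40 mg maintenance. At 41 kg, an 11-year-old would receive 41 × 40 = 1640 mg and a 12-year-old 1680 mg.

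**Precision of weight.** Protocol section 7.2.2 asks for weight in kilograms without saying to how many decimals. On the nominal basis, if weight is recorded to 0.1 kg, the affected values are 40.1 to 41.9 kg (+4.7% to +0.2%). If it is recorded in whole kilograms, the only affected recorded value is 41 kg (+2.4%). A true weight from 41.5 to just under 42 kg, recorded as 42, would still exceed the ceiling by up to 1.2%.

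**The case against.** The strongest reply is that this is one explanatory sentence in a background section. The operative rule is unambiguous and is the same wherever it appears, so no site would misdose because of it. Dose selection rested on Phase 2 efficacy, safety and pharmacokinetics, and the mg/kg ceiling only explains the cut-off. Enrolment was complete on 25 April 2019 (SAP section 1), so a new threshold cannot change dosing in this trial. All of that stands, and it is why the point is minor. It does not make the sentence correct: the cut-off lacks the property given as the reason for choosing it. A reader could take 40 kg as a rounded practical value, but neither document says so.

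A second objection is that 42 kg and 5% assume both trials count milligrams on the same basis. This also stands, and it limits how firmly a replacement threshold can be named. It does not remove the mismatch, because the reading that section 1.2.3 makes plausible enlarges it.

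A reader might go further and infer that light adolescents were overdosed or put at risk. The documents do not support that. Section 1.2.5 predicts exposures like those of the lower Phase 2 dose and reports no apparent safety differences for either Phase 2 dose relative to placebo. Section 1.2.3 also describes healthy volunteers given 40 mg/kg and then 20 mg/kg every 8 hours, which is more frequent dosing than here.

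**Conclusion.** Wrong as written, and minor. On nominal milligrams the ceiling is met from 42 kg. The excess is confined to subjects aged 12 and over weighing more than 40 and less than 42 kg, and stays just under 5%. This part is plain arithmetic on the protocol's own figures.

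The 44.6 kg and 11.4% figures are conditional. Section 1.2.3 gives the basis of the Phase 2 product strength but does not say on which basis the Phase 2 mg/kg doses were calculated. A reader should neither treat 11.4% as established nor treat 5% as a firm upper bound until that is known.

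The documents give no weight distribution, so the number of subjects concerned cannot be estimated and may be zero. No safety problem is shown, and nothing in the sample size, endpoints or analyses depends on the point.

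**What to change.** First, confirm whether the Phase 2 mg/kg doses were expressed as salt or as active moiety. Then correct the sentence in protocol section 1.2.5 to state the weight from which the ceiling is met and the excess below it. On the nominal basis it could read: for subjects aged 12 and over, the flat dose is at or below 40/20 mg/kg from 42 kg; above 40 and below 42 kg it is higher by less than 5%. On the salt basis, the figures become about 44.6 kg and up to about 11.4%.

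For any further dosing under this regimen, set the flat-dose cut-off at the confirmed weight wherever the rule appears (protocol sections 1.2.5, 3.1, 5, 5.4.2 and 6.2.1; SAP section 2.1). On the nominal basis that is 42 kg, where the flat and weight-based doses coincide and the step disappears. If the salt basis is confirmed, moving the cut-off is not enough by itself. The weight-based dose of 40/20 mg/kg would exceed the 37.7/18.9 mg/kg ceiling by 40/37.71 − 1 = 6.1%, and its cap already gives 1680/840 mg from 42 kg. The per-kilogram dose for subjects aged 12 and over would then need restating as well.

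For this trial the cost is one query and one corrected sentence. For later dosing on the nominal basis it is one changed threshold.
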